Eligible procedures: Procedures that would require local anesthesia include direct restorations (fillings), pulpotomy or pulpectomy (partial or complete removal of pulp) and placement of stainless steel crowns.

The standard of care in Department of Pediatric Dentistry is to administer nitrous before start of the treatment to alleviate patient anxiety. We will follow routine clinical protocol to titer the dose of nitrous oxide to individual patient needs.

Additionally, we hypothesize that the degree and depth of anesthesia would vary based on the initial disease state as well as the intended procedure. Accordingly, impact of the anesthesia will be analyzed at the completion of study using subgroup analysis.

Population 2: Symptomatic adults (>18 years) with symptomatic irreversible pulpitis

Location: Department of Endodontics, 2nd floor, Lyons Building

Eligible procedures:

Root canal treatment in teeth with significant decay but presenting with signs and symptoms of irreversible pulpitis (symptomatic)

Additional Inclusion Criteria:

- Tooth with a diagnosis of symptomatic irreversible pulpitis with or without periapical periodontitis
- Diagnosis is confirmed by history of spontaneous pain or prolonged (lingering) pain on application of cold or electronic pulp testing
- Tooth should have moderate to severe pain at the study onset (>54 on Heft Parker VAS scale)

Additional Exclusion criteria:

- Tooth with no response to cold / electronic pulp testing
- Tooth with periapical pathosis as seen in the radiograph
- Tooth with no vital coronal pulp tissue upon access

Population 3: Asymptomatic adults (>18 years) requiring restorations or crowns

Location: Department of General Practice, 2nd floor, Lyons/ Wood Building

Eligible procedures:

Direct and indirect restorations in teeth with significant decay but presenting with signs and symptoms of healthy pulp or reversible pulpitis

Additional Inclusion Criteria:

- Asymptomatic maxillary tooth with a diagnosis of primary or secondary dental caries extending more than 70% the thickness of dentin as seen in the radiograph

Additional Exclusion criteria:

- Tooth with no response to cold / electronic pulp testing
- Tooth with periapical pathosis as seen in the radiograph
- Endodontically treated tooth

Randomization

a. Sequence Generation:

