- b. Mild pain was defined as greater than 0 mm and less than or equal to 54 mm. Mild pain included the descriptors of faint, weak, and mild pain.
- c. Moderate pain was defined as greater than 54 mm and less than 114 mm.
- d. Severe pain was defined as equal to or greater than 114 mm. Severe pain included the descriptors of strong, intense, and maximum possible.

If study participants experience pain/ sensitivity/ discomfort at any time during the procedure (VAS >54), the local anesthesia would be considered a failure and rescue anesthetic (0.7 ml of articaine deposited at the periapex of the tooth of interest) administered to complete the intended procedure.

Secondary Outcome Measures in Adults:

- 1. Onset of meaningful anesthesia:** Patient will be given a stopwatch and will be instructed to press the watch at two different time points:
 - a. Onset of anesthesia (T-1 in min): Press the watch when they first perceive pain relief after the administration of local anesthetic
 - b. Significant pain relief (T-2 in min): Press the watch the second time when the patient report significant pain relief (<54 in VAS scale)

At each time of the stopwatch/ timer, the patient will record their pain in VAS scale. Treatment will proceed as long as the VAS rating is below 54mm. i.e. no to mild pain. If the pain is moderate to high at any point of the procedure (score of 54 or higher), the event would be considered anesthetic failure and a rescue anesthetic administered.

2. Spread of anesthesia:

The teeth and the soft tissues on the side of the mouth ipsilateral to the tooth of interest will be evaluated for spread of anesthesia. The number of teeth that are anesthetized will be counted after cold and electronic pulp tests and recorded (maximum possible score is 5). Similarly, the buccal and lingual gingiva will be tested for anesthesia 1 cm below the gingival margin for each of the 5 teeth ipsilateral to the tooth of interest (maximum score of 5). The hard tissue and soft tissue scores will be compared between two groups.

3. Duration and depth of anesthesia:

In addition to the initial onset, we would gather information about the depth of anesthesia (as tested by EPT and cold tests) at 15 min, 30 min and 1 hour after administration of anesthesia. This would help us identify the duration for which reliable pulpal anesthesia is maintained.

4. Anxiety in Adults:

Modified Dental Anxiety Scale (MDAS):

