5. What is the most important deciding factor for you to choose NASAL SPRAY ANESTHETIC for your dental needs?

Cost Fear and Anxiety

6. How much extra money would you be willing pay for the NASAL SPRAY ANESTHETIC?

\$20 \$50 Up to \$100 It is not worth paying extra

7. Did your experience with the NASAL SPRAY ANESTHETIC change your outlook towards receiving future dental care?

Nothing changed; Still scared of dental visits This appointment was better but am still concerned about my future visits This appointment definitely eased my apprehension of future dental visits

8. If you had known that there was an option of NASAL SPRAY ANESTHETIC, would you have sought dental care early?

Definitely No Maybe Definitely Yes

5. Survey after 24 hours:

A short one question about the side effects of local anesthetic will be asked to the patient in person or over phone at 24 hours.

Did you suffer any of the following side-effects after your dental visit?

- nasal drainage,
- nasal congestion,
- burning,
- pressure,
- sinus congestion,
- pain and soreness at the site of the anesthesia (scored from 1-10)
- Numbing or tingling in throat
- other (Specify)_____

Flow of research study visit in adults (>18 years):

Screening of EHR will be done to identify potential study participants on a routine clinical visit. During the study visit the study related procedures would be preformed in the following order:

1. Go over the study details, answer participant questions and obtain informed consent
2. Administer MDAS anxiety survey
3. Ask patient to rate pain (if present) in the Heft Parker Scale
4. Reveal allocation (Kovanaze or Articaine)
5. Take baseline BP and heart rate
6. Administer local anesthetic
7. Wait for patient to signal achievement of meaningful anesthesia (using stop watch)
8. Map the extent of soft tissue and hard tissue anesthesia in data collection form
9. Proceed with the intended procedure
10. Assign anesthetic **failure** if subject perceives pain after start of procedure. Record the failure in data collection form and proceed with rescue anesthetic to complete the procedure
11. Assign anesthetic **success** if local anesthesia was adequate to complete the intended procedure without need for rescue anesthetic. Record in data collection form
12. Administer MDAS survey for all participants
13. Administer satisfaction questionnaire to subjects in Kovanaze group only
14. Take end of appointment BP and heart rate

Primary Outcome Measure in Children:

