2. Mild, soft verbal protest or (quiet) crying as a signal of discomfort, but does not obstruct progress. Appropriate behavior for procedure, i.e., slight start of injection, "ow" during drilling if hurting, etc.
3. Protest more prominent. Both crying and hand signals. May move head around making it hard to administer treatment. Protest more distracting and troublesome. However, child still complies with request to cooperate.
4. Protest presents real problem to dentist. Complies with demands reluctantly, requiring extra effort by dentist. Body movement.
5. Protest disrupts procedure, requires that all of the dentist's attention be directed toward the child's behavior. Compliance eventually achieved after considerable effort by dentist, but without much actual physical restraint. (May require holding child's hands or the like to start). More prominent body movement.
6. General protest, no compliance or cooperation. Physical restraint is required.

Flow of research related procedures on study visit in children:

Screening of EHR will be done to identify potential study participants on a routine clinical visit. During the study visit the study related procedures would be performed in the following order:

1. Go over the study details, answer participant questions and obtain informed consent
2. Administer STAI-Y6 questionnaire
3. Ask patient to rate pain (if present) in the Emoji Scale
4. Reveal allocation (Kovanaze or Articaine)
5. Take baseline BP and heart rate
6. Administer local anesthetic
7. Wait for patient to signal achievement of meaningful anesthesia (using stop watch)
8. Map the extent of soft tissue and hard tissue anesthesia in data collection form
9. Proceed with the intended procedure
10. Assign anesthetic **failure** if subject perceives pain after start of procedure. Record the failure in data collection form and proceed with rescue anesthetic to complete the procedure
11. Assign anesthetic **success** if local anesthesia was adequate to complete the intended procedure without need for rescue anesthetic. Record in data collection form
12. Record patient anxiety and behavior using Venham scale
13. Take end of appointment BP and heart rate

References:

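### Onset times T-1 and T-2 are undefined for participants without baseline pain, and adult treated-tooth readings after rescue or pulp removal do not measure the assigned agent

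*Combined protocol and SAP*

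**What the plan says.** **Onset.** Secondary Outcome Measures in Adults, item 1, gives one definition for all adults. For T-1 the participant is told to "Press the watch when they first perceive pain relief after the administration of local anesthetic". T-2 is pressed "when the patient report significant pain relief (<54 in VAS scale"). The same item adds: "Treatment will proceed as long as the VAS rating is below 54mm". Children have the same T-1 instruction and a T-2 on the emoji scale.

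**Who has pain at entry.** Only Population 2 has a pain criterion: "Tooth should have moderate to severe pain at the study onset (>54 on Heft Parker VAS scale"). Population 3 requires "Asymptomatic maxillary tooth with a diagnosis of primary or secondary dental caries". Population 1 has no pain criterion. Step 3 of the adult visit flow reads "Ask patient to rate pain (if present) in the Heft Parker Scale", and step 3 of the children's flow reads "Ask patient to rate pain (if present) in the Emoji Scale".

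**Place in the visit.** Step 7 of both flows is "Wait for patient to signal achievement of meaningful anesthesia (using stop watch"). Mapping of hard and soft tissue follows at step 8 and the procedure at step 9.

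**Duration (adults only).** Item 3 plans EPT and cold readings at 15, 30 and 60 minutes after dosing, to learn how long reliable pulpal anesthesia lasts. It names no tooth, and the readings do not appear in the adult visit flow. Rescue in either arm is articaine at the apex of the treated tooth. Step 10 records the failure but does not ask for its time. Population 2 undergoes root canal treatment.

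**The concern.** T-1 and T-2 time the relief of pain. A participant with no pain has no relief to report, so T-1 has no event to time. A pain-free adult is below 54 mm before any drug is given, so T-2 does not depend on the agent. If such participants press the watch anyway, the recorded times mean something the plan has not defined, and they would sit beside Population 2 times under the same label.

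The duration readings raise a separate problem, which arises only if the treated tooth is the one read. After rescue, a numb tooth may reflect the rescue articaine. In the articaine arm it reflects the assigned dose plus more of the same drug. After pulp removal, no response is expected whichever agent was given. Without a handling rule, a post-rescue reading would be credited to the assigned agent, which tends to flatter the arm rescued more often.

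**Working it through.** **The plan's own figure.** The plan states no figure for onset or duration. Its one calculation, 38 per group, is for the primary outcome. With 78% success assumed in both arms, a margin of 0.25, one-sided alpha 0.05 and power 83%, n = 2 × 0.78 × 0.22 × (1.645 + 0.954)² / 0.25² = 37.1, rounded up to 38. It reproduces under that assumption and is not affected by this point.

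**Onset, case by case.**
- Population 2: baseline above 54 mm is required. T-1 and T-2 both have an event to time.
- Pain-free adult (0 mm), as expected in Population 3: T-1 has no event. Since 0 < 54, T-2 is met before dosing.
- Adult with mild pain: T-1 can occur. A baseline below 54 mm already meets T-2.
- Pain-free child: T-1 has no event. The children's section treats scores below 4 as painful in the primary outcome, but as no to mild pain in the rule for proceeding, while T-2 needs a score above 4. If low means painful, T-2 is met at baseline. If low means no pain, T-2 cannot be reached through relief. It is uninformative either way.

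**How many.** The sample size section plans 90 per population (45 + 45). Adults are Populations 2 and 3: 2 × 90 = 180. Population 3 is 90/180 = 50%, a planned maximum that is reached only if every Population 3 participant is pain-free. The number of pain-free children is not given and lies between 0 and 90.

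**Duration: which readings are affected.**
- Before rescue and before pulp removal: unaffected.
- Untreated teeth outside the rescue infiltration: unaffected.
- Treated tooth after rescue, pulp present: assigned agent and rescue are mixed.
- Treated tooth after pulp removal (Population 2): uninformative in both arms, with or without rescue.

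**Illustration for the third case.** Primary success is completion without rescue, so a 25-point deficit in success is a 25-point excess of rescue. Assume the same share of rescued participants in each arm is misread, meaning counted as numb from the assigned agent when rescue caused it. Then

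shift between arms = share misread × (Kovanaze rescue rate − articaine rescue rate).

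- One misread participant: 1/45 = 2.2 points in that arm.
- Equal rescue rates: 0.
- Difference 25 points, half misread: 0.5 × 25 = 12.5 points, or 45 × 0.125 = 5.6 participants.
- Difference 25 points, all misread: 1 × 25 = 25 points, or 45 × 0.25 = 11.25 participants.

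The shift favours Kovanaze if Kovanaze is rescued more, and the sign reverses if articaine is. If the misread share differs between arms, the shift is not limited to the difference in rescue rates.

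**The case against.** The outcome is headed as onset of meaningful anesthesia, and step 7 asks for a signal of anesthesia, so a pain-free participant could sensibly press the watch on feeling numb. This stands against the stronger reading that onset carries no information at all in Population 3. It does not rescue the endpoint, because the instruction given is about pain relief. Numbness times would be a different, unstated endpoint.

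Population 3 also admits signs and symptoms of reversible pulpitis, and baseline pain is rated where present. The 90 adults are therefore a ceiling, not a count.

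A reader might infer that treatment starts too early in pain-free participants and that the primary outcome is biased. The documents do not support this. The sentence on proceeding below 54 mm leads into what happens during the procedure and can be read as a rule for continuing. Step 7 separately requires a signal. What that signal means without pain is unclear and needs reconciling, but no effect on the primary outcome can be shown.

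A reader might also infer that all the duration readings are compromised, or that the 12.5 to 25 points apply to both adult populations. Neither follows. The plan names no tooth, and the spread outcome just before it tests five. After pulp removal the reading is uninformative in both arms, so misread rescue adds nothing. Rescue is triggered by reported pain, not by EPT or cold response, so a rescued tooth may already have been unresponsive and the misread share may be well below one. The plan also states no between-arm test of duration. These limits stand, and they make the duration part conditional.

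**Conclusion.** The onset part holds on the text. As defined, T-1 has no event in a pain-free participant, and T-2 is met before dosing in a pain-free adult. This affects up to 90 of 180 planned adults and between 0 and 90 children.

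The duration part holds conditionally. If the treated tooth is read, readings after rescue, or after pulp removal in Population 2, do not measure the assigned agent, and no rule covers them. The illustrated shift of 0 to 25 points applies only to treated-tooth readings after rescue with the pulp still present, mainly in Population 3. It rests on an assumed difference in rescue rates of 0 or 25 points and an equal misread share. The trial's actual rescue rates are not known from the documents.

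Both parts concern secondary outcomes. The sample size is unchanged. The correction is worth making because it is cheap and, for rescue and pulp-removal times, may not be recoverable afterwards.

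**What to change.** **Onset**
- Analyse T-1 only in participants with some baseline pain.
- Analyse T-2 only in those whose baseline pain is on the painful side of the cut: Population 2, and such children once the contradictory emoji directions are reconciled.
- For everyone else, report the step-8 pre-procedure cold/EPT status of the study tooth, labelled as anesthesia status and not as an onset time. The spread outcome is described as a count of teeth, so the form should hold the study tooth's own result.
- Reconcile the step-7 signal in both visit flows with the entry criteria, and state what it means for a participant without pain. Step 8 follows that signal, so the status reading depends on it.

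**Duration (adults)**
- Name the tooth or teeth read at 15, 30 and 60 minutes, and add the readings to the visit flow.
- Record the clock times of rescue and of pulp removal.
- Do not credit treated-tooth readings after rescue to the assigned agent. Make the main summary *no cold/EPT response and not rescued*, in line with the plan's own definition of rescue as anesthetic failure.
- Treat treated-tooth readings after pulp removal as not evaluable.
- Report the numbers rescued and not evaluable by arm and time.

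**Cost.** Rewording of two secondary outcomes and of step 7 in two flows, the readings added to the adult flow, the study tooth's own step-8 result, and two time fields. Pain-free participants will have no onset time. Population 2 will have fewer evaluable late readings. The timing of pulp removal may differ with rescue, so the evaluable denominator may differ between arms and must be shown. The main summary also carries the primary outcome's failure into a secondary one, and its label should make that plain.

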- Maximum blood pressure reading of 166/100 mmHg
- Vital pulp (Cold and EPT positive)

Exclusion Criteria:

- History of inadequately controlled hypertension or active thyroid disease
- Five or more nosebleeds in the past month
- Known allergy to oxymetazoline, tetracaine, benzylalcohol or para-aminobenzoic acid
- History of congenital or idiopathic methemoglobinemia
- Taking monoamine oxidase inhibitors, tricyclic antidepressants (e.g. amitriptyline), or non-selective beta adrenergic antagonists (e.g. propranolol)
- Taking oxymetazoline-containing products (i.e., Afrin) in the last 24 hours

- Pregnant and lactating women
- Non vital pulp (Cold and EPT negative)

Study Characteristics:

Design:

Randomized, open label clinical trial

Non-inferiority threshold and Sample size calculation:

The anesthetic efficiency of articaine has been reported in the literature to be around 78 – 88% (Evans et al.). The non-inferiority threshold is the maximum allowable excess of outcome events arising from the novel treatment compared with the standard treatment. The threshold for this study has been selected based on draft guidance set by the FDA (Temple et al.) and was set at 25%. Using nQuery Advisor v7.0, we verified that a sample size of 38 subjects per group would be needed to show a non-inferiority of <25% (one sided alpha of 0.05 and a power of 83%).

Accordingly, each of our study arms will have 90 subjects: 45 in Kovanaze and 45 in Articaine groups.

Accounting for screen failures and dropouts, we will recruit 100 participants in each population totaling 300 for the entire study.

Intervention:

Metered Kovanaze sprays (0.2 ml each spray, St. Renatus) in the nostril on the same side as the tooth of interest. The dose involves:

2 sprays in adult and kids weighing 40 kg or more

1 spray in kids > 6 years but weighing between > 20 kg and < 40 kg

Control:

- Children: 1.0 ml of 4% articaine (containing 1:100000 epinephrine) delivered in the periapex of the tooth of interest by labial/buccal infiltration
- Adults: 1.8ml of 4% articaine (containing 1:100000 epinephrine) delivered in the periapex of the tooth of interest by labial/buccal infiltration

Population:

Our study will evaluate the effectiveness of Kovanaze in three different populations.

Population 1: *Children (aged 6-17 years and weighing >20 kg) requiring specific procedures for treatment of oral disease*

Location: Department of Pediatric Dentistry, 3rd floor, Wood Building

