The Modified Dental Anxiety Scale (MDAS) consists of 5 questions each with a 5-category rating scale, ranging from 'not anxious' to 'extremely anxious'. This answering scheme is a simplified rating system in comparison with Corah's Dental Scale that was an early 4-question measure of dental anxiety. The MDAS has an extra item about the respondent's anxiety to a local anesthetic injection that is particularly relevant for this study. (Humphris et al). Cut off is 19 or above (out of 25) for questions 1-5, which indicates a highly dentally anxious patient, possibly dentally phobic. Questions 6-8 are specific to this study to assess the effect of Kovanaze on dental anxiety.

CAN YOU TELL US HOW ANXIOUS YOU GET, IF AT ALL, WITH YOUR DENTAL VISIT BY INSERTING 'X' IN THE APPROPRIATE BOX?

- 1. If you went to your Dentist for TREATMENT TOMORROW, how would you feel?**

Not *Slightly* *Fairly* *Very* *Extremely*
Anxious *Anxious* *Anxious* *Anxious* *Anxious*

2. If you were sitting in the WAITING ROOM (waiting for treatment), how would you feel?

Not *Slightly* *Fairly* *Very* *Extremely*
Anxious *Anxious* *Anxious* *Anxious* *Anxious*

3. If you were about to have a TOOTH DRILLED, how would you feel?

Not *Slightly* *Fairly* *Very* *Extremely*
Anxious *Anxious* *Anxious* *Anxious* *Anxious*

4. If you were about to have your TEETH SCALED AND POLISHED, how would you feel?

Not *Slightly* *Fairly* *Very* *Extremely*
Anxious *Anxious* *Anxious* *Anxious* *Anxious*

5. If you were about to have a LOCAL ANAESTHETIC INJECTION in your gum, above an upper back tooth, how would you feel?

Not *Slightly* *Fairly* *Very* *Extremely*
Anxious *Anxious* *Anxious* *Anxious* *Anxious*

4. Satisfaction Questionnaire (for KOVANAZE Participants only)

These questions are to be administered at the end of the study visit to participants in Kovanaze arm only:

1. Have you ever experienced a LOCAL ANESTHETIC INJECTION in your gum, for dental treatment?

Yes No

2. When was the last time you received a LOCAL ANESTHETIC INJECTION in your gum?

> 1 year 6 months ago Less than a month ago

3. Compared to INJECTION, how effective do you think was NASAL SPRAY ANESTHETIC in reducing your anxiety and comfort during dental procedure?

Not Effective Slightly Effective No Difference Very Effective Extremely Effective

4. How likely is it that you would ask your dentist for a NASAL SPRAY ANESTHETIC, for your future treatment needs (compared to needle anesthetic)?

Never No preference Every time

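### The Kovanaze satisfaction form asks about injection history without excluding that day's rescue articaine, and items 2 and 5 lack options some respondents will need

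*Combined protocol and SAP*

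**What the plan says.** Acceptability of Kovanaze is part of the second Specific Aim. The instrument is the Satisfaction Questionnaire among the adult secondary outcomes. On timing, the plan says "These questions are to be administered at the end of the study visit to participants in Kovanaze arm only". In the adult visit flow this is step 13: "Administer satisfaction questionnaire to subjects in Kovanaze group only".

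Rescue comes earlier. At step 10 a failure is recorded and staff "proceed with rescue anesthetic to complete the procedure". The Primary Outcome Measure in Adults describes it: "rescue anesthetic (0.7 ml of articaine deposited at the periapex of the tooth of interest) administered to complete the intended procedure". The control articaine is "delivered in the periapex of the tooth of interest by labial/buccal infiltration".

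Item 1 reads "Have you ever experienced a LOCAL ANESTHETIC INJECTION in your gum, for dental treatment", with yes or no as answers. Item 2 asks when the last such injection was. Its options are more than one year, then "6 months ago Less than a month ago" (two options, run together in the extracted text). Item 3 asks for a rating of the spray compared with injection. Item 4 asks about future preference. Item 5 asks for the most important factor in choosing the spray and offers "Cost Fear and Anxiety", again two options run together. The plan gives no scoring or analysis for any of these items.

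**The concern.** Items 1 and 2 are background questions. They show who has earlier experience of a dental injection, and so who can meaningfully answer item 3, which sets the spray against injection. Asked after rescue and without a time limit, they mix earlier experience with what happened minutes before. The mixing is not spread evenly: it falls only on participants in whom the spray failed, whose views on acceptability are likely to differ most from the rest.

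The option lists raise a separate problem that does not depend on rescue. Some truthful answers to item 2 have no box. Item 5 can return only two reasons, so its result is largely fixed by the form. At stake is the reading of part of the second aim, in particular the comparison with injection and the stated reason for choosing the spray.

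**Working it through.** The plan states no figure on this point, so there is none to reproduce. The check has three parts.

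**1. Order of events and literal answers.** Rescue is step 10 and the questionnaire step 13. The documents do not call the rescue an injection. That is inferred: it is the control drug, placed at the same site at which the control is given by infiltration into the gum. On that reading, the literal answers are:

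| History before the visit | Not rescued: item 1 / item 2 | Rescued: item 1 / item 2 |
|---|---|---|
| Never injected | No / no true option | Yes / under a month |
| Under one month ago | Yes / under a month | Yes / under a month |
| Between one and six months ago | Yes / no true option | Yes / under a month |
| Six months ago | Yes / six months | Yes / under a month |
| Between six months and one year ago | Yes / no true option | Yes / under a month |
| Over one year ago | Yes / over one year | Yes / under a month |

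The rescued column is constant, so item 2 cannot separate one history from another in that group. As a record of earlier history, item 1 is wrong only in the first row, and item 2 is right only in the second.

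**2. How many are exposed.** The sample size section gives 45 Kovanaze participants per population. Two populations are adult, so 2 × 45 = 90. Expected number rescued = 90 × (1 − success rate):

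- 90% success (Background, upper figure): 90 × 0.10 = 9.
- 83% success (Background, lower figure): 90 × 0.17 = 15.3.
- 78% success (assumed; the low end of the articaine range in the sample size section): 90 × 0.22 = 19.8.
- 53% success (assumed; 78% less the 25-point margin): 90 × 0.47 = 42.3.

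Even at 90% success, the chance of at least one rescue among the 45 in one adult population is 1 − 0.90^45 = 0.991.

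**3. The option lists.** Item 2 has no option for never and no skip after a no on item 1. Between one month and one year, its only category is six months. Item 5 has no place for pain of injection, effectiveness, another reason, or not choosing the spray. The plan's own Background names fear of pain, as well as fear of injections, as a reason for avoiding the dentist, and its 24-hour side-effect survey does have a free-text category for other answers.

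**The case against.** The strongest reply is that this is a descriptive survey in one arm, with no hypothesis test, and that most of it works. Item 4 lets a respondent say never, item 6 that the spray is not worth extra money, item 7 that nothing changed, and item 8 definitely no. Items 7 and 8 bear most directly on the survey's stated purpose, confidence in seeking care, and are not faulted here. Failure and rescue are already recorded at steps 10 and 11, so affected respondents can be identified. All of this stands, and it limits the point. It does not recover a rescued participant's earlier history or widen item 5.

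A respondent might also discount that day's rescue when answering items 1 and 2. That is possible, but the wording does not ask for it, and the form would not show who did.

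Four stronger readings are tempting, and the documents do not support them:

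- That 9 to 15 participants would be misrecorded. Those are expected rescues. The documents give no rate of earlier injection, so the number misrecorded cannot be derived.
- That item 4 is invalid for people never injected. It asks about future preference, which they can still state. Item 3 is the comparison that depends on earlier experience.
- That item 6, by presuming extra cost, forces item 5 towards fear. Item 6 comes after item 5, and a respondent may leave item 5 blank.
- That the acceptability results as a whole are set by the form. Only item 5 is constrained in that way.

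**Conclusion.** The point holds as a defect in the instrument, minor in weight. Items 1 and 2 do not record earlier injection history for rescued participants: item 2 loses its information for all of them, and item 1 is wrong for those with no earlier injection. Item 2 is not exhaustive for anyone, and item 5 cannot record several plausible reasons.

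The group at risk is about 9 to 15 of 90 Kovanaze adults if the Background's 83 to 90% applies, and about 20 at an assumed 78%. The cited rates are background literature figures, not planning assumptions for these populations. Half of the 90 are to have symptomatic irreversible pulpitis, so the count could differ. The conclusion also assumes that the rescue is given by injection and that no response options were lost when the text was read from PDF; nothing in the text suggests that any were. How common the missing answers would be is unknown. A reader should not carry this over to the primary outcome, the non-inferiority test or the sample size, none of which uses this form.

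**What to change.** - **Items 1 and 2:** limit both to the time before that day's visit, or ask them before treatment.
- **Item 2:** use complete, non-overlapping ranges and add an option for never.
- **Item 3:** add a not-applicable option for people who had never had an injection before that day. Leave item 4 open to everyone.
- **Item 5:** add pain of injection, effectiveness, other (to be specified) and would not choose the spray.
- **Reporting:** present items 3 to 8 separately for participants with and without rescue, using the status already recorded at steps 10 and 11.

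The cost is a form revision and a slightly longer questionnaire, with no added visits or participants. If the form is already in use, reporting by rescue status is still possible, and the limits of items 1, 2 and 5 should be stated with the results.
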